8.0 INCLUSION/ EXCLUSION CRITERIA

8.1 Inclusion Criteria

1. Informed Consent

- a. Ability to provide written informed consent in accordance with federal, local, and institutional guidelines

2. Target Population

- a. Documented histological or cytological diagnosis of renal cell carcinoma with a clear-cell component
- b. Age \geq 18 years
- c. Karnofsky Performance Score (KPS) \geq 70% ([Attachment 4](#))
- d. Estimated Life Expectancy of at least 3 mo
- e. Measurable Disease per RECIST 1.1 as determined by the Investigator (see [Attachment 5](#))
- f. One and not more than two prior systemic lines of therapy (monotherapy or combination regimen) for advanced or metastatic RCC
 - 1) Must include either:
 - i. one anti-angiogenic therapy (any VEGF pathway-targeted agent, used either as monotherapy or as a component of a combination regimen)
– OR –
 - ii. the combination regimen of nivolumab + ipilimumab
 - 2) Exposure to a prior treatment regimen for \geq 4 weeks is considered a prior line of therapy, regardless of reason for its discontinuation (exception: high-dose IL2 will count as prior therapy if $>$ 3 doses administered)
 - i. 4 weeks will be counted from first to last dose for regimens that are intended to be administered on daily schedules (e.g., sunitinib, pazopanib) and from first dose to end of cycle length after last dose for regimens that are intended to be administered in intervals of \geq 1 week (e.g., one treatment of a Q2W regimen counts as 2 weeks of therapy)
 - 3) Rechallenge with the same agent or regimen will not be considered a new line of therapy, if the patient had not previously discontinued that agent or regimen because of disease progression
 - 4) Systemic adjuvant therapy is considered a prior line of therapy if the patient has disease recurrence on or within 1 year after the last dose of adjuvant therapy
- g. The patient must have had radiographic evidence of disease progression on or after the most recent systemic therapy and within 6 mo before randomization

3. Laboratory Findings

- a. Serum creatinine \leq 2.0 \times upper limit of normal or calculated creatinine clearance (C_{Cr}) \geq 30 mL/min (\geq 0.5 mL/sec) using the Cockcroft-Gault equation:

$$C_{Cr} = \{((140 - \text{age}) \times \text{actual body weight}) / (72 \times S_{Cr})\} \times 0.85 \text{ (if female)}$$

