14.6.3 Additional Endpoints

Overall Response Rate (ORR)

ORR is defined as the percentage of patients with CR or PR according to the RECIST 1.1 criteria. Response will be adjudicated by the IRC, and response confirmation is not required to compare the two arms in this double-blind protocol. Patients with no evaluable on-study response assessments will be regarded as non-responders. The ORR will be compared between treatment arms by both the Fisher's exact test and a logistic regression analysis accounting for the randomization stratification factors.

Duration of Response (DOR)

For patients achieving a PR or a CR, the duration of response will be calculated as the time between the first documentation of a PR or a CR to the first documentation of PD or death, whichever occurs first. For patients achieving first a PR then a CR, the PR date will be the starting date for response duration calculation. For responders for whom a PD has not been documented yet, [Section 14.6.1](#) conventions regarding PFS censoring will apply. Response duration will be descriptively presented for responders in each treatment arm.

Disease Control Rate (DCR)

DCR is defined as the summed percentage of patients with CR, PR or SD documented at least 8 weeks (-5 day window) following randomization according to RECIST v1.1 criteria.

Patient Reported Outcomes

Patients will be assessed using the NCCN-Functional Assessment of Cancer Therapy (FACT) Kidney Symptom Index ([FKSI-19](#)) questionnaire and the EuroQoL 5D utility score ([EQ-5D-5L](#)) and compared between the two treatment arms. Details of the planned analyses for these outcomes will be provided in the SAP.

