- If it is the opinion of the radiologist that the lesion has likely disappeared, the measurement should be recorded as 0 mm. If the lesion is believed to be present and is faintly seen but too small to measure, a default value of 5 mm should be assigned and BML (below measurable limit) should be ticked (Note: It is less likely that this rule will be used for lymph nodes since they usually have a definable size when normal and are frequently surrounded by fat such as in the retroperitoneum; however, if a lymph node is believed to be present and is faintly seen but too small to measure, a default value of 5 mm should be assigned in this circumstance as well and BML should also be ticked).

This default value is derived from the 5 mm CT slice thickness (but should not be changed with varying CT slice thickness). The measurement of these lesions is potentially non-reproducible, therefore providing this default value will prevent false responses or progressions based upon measurement error.

To reiterate, however, if the radiologist is able to provide an actual measure, that should be recorded, even if it is below 5 mm and in that case BML should not be ticked. (BML is equivalent to a less than sign <)

Lesions that split or coalesce on treatment: When non-nodal lesions ‘fragment’, the longest diameters of the fragmented portions should be added together to calculate the target lesion sum. Similarly, as lesions coalesce, a plane between them may be maintained that would aid in obtaining maximal diameter measurements of each individual lesion. If the lesions have truly coalesced such that they are no longer separable, the vector of the longest diameter in this instance should be the maximal longest diameter for the ‘coalesced lesion’.

Evaluation of non-target lesions

This section provides the definitions of the criteria used to determine the tumor response for the group of non-target lesions. While some non-target lesions may actually be measurable, they need not be measured and instead should be assessed only qualitatively at the time points specified in the protocol.

Complete Response (CR): Disappearance of all non-target lesions and normalization of tumor marker level. All lymph nodes must be non-pathological in size (< 10 mm short axis).

Non-CR/Non-PD: Persistence of one or more non-target lesion(s) and/or maintenance of tumor marker level above the normal limits.

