(18)F-Fluorodeoxyglucose Positron Emission Tomography (FDG-PET) For the purposes of this study, progressive disease *should not* be made solely on FDG-PET findings because the mechanism of the study drug, CB-839, may affect glucose metabolism in both normal and tumor tissues. All FDG-PET findings suggestive of progressive disease should be confirmed by dedicated anatomic imaging (CT or MRI). The following modifications to RECIST v1.1. will be applied to this study:

- Negative FDG-PET at baseline, with a positive FDG-PET at follow-up is a sign of PD based on a new lesion. *Confirmation of the new lesion by CT or MRI scan is required per protocol.

- No FDG-PET at baseline and a positive FDG-PET at follow-up:
 - If the positive FDG-PET at follow-up corresponds to a new sign of disease confirmed by CT, this is PD
 - If the positive FDG-PET at follow-up is not confirmed as a new site of disease on CT, additional follow-up CT scans are needed to determine if there is truly progression occurring at that site (if so, the date of PD will be the date of the initial abnormal *CT scan).
 - If the positive FDG-PET at follow-up corresponds to a pre-existing site of disease on CT that is not progressing on the basis of the anatomic images, this is not PD.

*reflects study-specific modification to RECIST v.1.1

Time point response

It is assumed that at each protocol specified time point, a response assessment occurs. [Table A](#) provides a summary of the overall response status calculation at each time point for patients who have measurable disease at baseline.

Missing assessments and not-evaluable designation

When no imaging/measurement is done at all at a particular time point, the patient is not evaluable at that time point. If only a subset of lesion measurements are made at an assessment, usually the case is also considered not evaluable at that time point, unless a convincing argument can be made that the contribution of the individual missing lesion(s) would not change the assigned time point response. This would be most likely to happen in the case of PD. For example, if a patient had a baseline sum of 50 mm with three measured lesions and at follow-up only two lesions were assessed, but those gave a sum of 80 mm, the patient will have achieved PD status, regardless of the contribution of the missing lesion.

Table A: Time Point Response: Patients with Targets (+/- Non-Target) Disease

Target Lesions	Non-Target Lesions	New Lesions	Overall Response

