To prevent a stratification cell having too few events, if a stratification cell has less than 10 PFS events (two arms combined), the stratification factor that contributes the least number of events for that cell will be removed. Stratification factors for the analyses will be removed until all stratification cells have at least 10 PFS events in two arms combined.

As a sensitivity analysis, the above analyses will be performed using the number of prior TKI cancer therapy (0 vs. ≥ 1) and IMDC prognostic risk group (favorable vs. intermediate vs. poor) and prior PD-1/PD-L1 inhibitor therapy as the stratification factors.

If there is notable imbalance in number of prior lines of anti-cancer therapy between the two treatment arms and if sample size permits, sensitivity analysis will be performed using number of prior lines of anti-cancer therapy (1 vs. 2) and IMDC prognostic risk group (favorable vs. intermediate vs. poor) and prior PD-1/PD-L1 inhibitor therapy as the stratification factors.

Similarly to the primary analysis, to prevent a stratification cell having too few events, if a stratification cell has less than 10 PFS events (two arms combined), the stratification factor of prior PD-1/PD-L1 inhibitor therapy will be removed.

Results from an unstratified analysis will also be provided.

Table 4 Censoring Rules for Progression Free Survival

Situation	Date of PFS Event or Censoring	Outcome
No baseline disease assessment	Date of randomization	Censored
No post-baseline assessments and no death	Date of randomization	Censored
No progression and no death	Date of last evaluable tumor assessment	Censored
Additional cancer therapy prior to documentation of disease progression or death	Date of last evaluable tumor assessment before initiation of additional cancer therapy	Censored
Documented RECIST v1.1 progression or death between scheduled visits [1]	First date of documented progression or death	PFS event
RECIST v1.1 progression or death documented to occur following missing at least 2 consecutive scheduled radiographic disease assessments (including missing assessments, insufficient data for the assessments, and an overall response of non-evaluable) following previous evaluable radiologic tumor assessment	Date of last tumor assessment with no documented progression [2]	Censored [2]

RECIST v1.1, Response Evaluation Criteria in Solid Tumors Version 1.1

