6.5.3.2 Duration of Response

Duration of Response (DOR) is defined for patients achieving a PR or a CR as the time from the first documented overall response (PR or CR) to the first documented PD as assessed by the IRC according to RECIST v1.1 or death from any cause, whichever

occurs first. Patients who are alive and who have not experienced disease progression at the time of the analysis will be censored at the date of the last evaluable tumor assessment. If no tumor assessments were performed after the date of the first occurrence of the overall response (CR or PR), DOR will be censored at the date of the first occurrence of the overall response. Censoring rules for DOR will follow those in [Table 4](#). The determination of DOR is based on a non-randomized subset of patients (confirmed responders only), and formal hypothesis testing will not be performed. The subset of responders are defined based on post randomization outcomes therefore the responder population is not balanced across the two treatment arms. DOR will be estimated using Kaplan Meier (KM) methodology. Comparisons between treatment arms will be made using the stratified and unstratified log-rank test for descriptive purposes only.

DOR will be reported for patients with confirmed ORR.

6.5.3.3 *Disease Control Rate*

Disease Control Rate (DCR) is defined as the summed percentage of patients with CR, PR or stable disease (SD) documented following randomization according to RECIST v1.1 per IRC.. DCR will be analyzed the same way as ORR.

6.5.3.4 *PFS and OS Rates at Landmark Timepoints*

The PFS rates (according to RECIST 1.1 criteria per IRC) at 6-month, 9-month, and 1-year timepoints are defined as the probabilities the patients are alive and progression free at those timepoints after randomization. The OS rates at 1- and 2- and 3-year landmark timepoints are defined as the probabilities that patients are alive at those time points after randomization. The PFS and OS rate at the landmark timepoints after randomization within the ITT population will be estimated for each treatment arm using Kaplan-Meier methodology, along with 95% CI calculated with the standard error derived from the Greenwood formula.

6.5.3.5 *Patient Reported Outcomes*

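### The disease control rate omits Non-CR/Non-PD, so a non-progressing patient in whom the IRC finds no target lesion is scored as a failure

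*Protocol*

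**What the plan says.** **Entry.** Protocol 8.1, criterion 2e, requires "Measurable Disease per RECIST 1.1 as determined by the Investigator". Neither document asks the IRC to confirm measurability before randomization.

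**Assessment.** For ORR, Protocol 14.6.3 states: "Response will be adjudicated by the IRC, and response confirmation is not required to compare the two arms in this double-blind protocol". SAP 4.1.1.3 and 6.5.3.3 place DCR with the IRC as well.

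**Categories.** Attachment 5 of the Protocol defines PR and SD by changes in the sum of target-lesion diameters. Persisting non-target disease has its own category, Non-CR/Non-PD, whose entry begins "Persistence of one or more non-target lesion(s". The only time-point table is headed "Table A: Time Point Response: Patients with Targets (+/- Non-Target) Disease"; according to the text that introduces it, it "provides a summary of the overall response status calculation at each time point for patients who have measurable disease at baseline".

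**Endpoint.** SAP 6.5.3.3 defines DCR as "the summed percentage of patients with CR, PR or stable disease (SD) documented following randomization" and analyses it in the same way as ORR. Under SAP 6.5.3.1 that means the ITT population, with anyone who does not meet the criteria counted on the failure side.

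**The concern.** Eligibility and endpoint rest on different readers. A patient can enter on the investigator's reading and then have no target lesion on the IRC's reading. That patient stays in the ITT denominator.

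For ORR the failure rule causes no difficulty, because disease that merely persists is not a response. Carried over to DCR, the same rule misfires. The patient's disease is present and not progressing, which is what DCR is meant to capture, but the applicable category is missing from the numerator. DCR is then too low in both arms, by an amount that depends on how often the two readings of measurability differ rather than on treatment.

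**Working it through.** The plan gives no figure for DCR or for the share of patients without an IRC target lesion. The first part of the check is therefore on definitions, and the second uses assumed shares.

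**1. Two non-progressing patients side by side**

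| | IRC finds a target lesion, stable | IRC finds no target lesion |
|---|---|---|
| Non-target disease | persists, no PD | persists, no PD |
| New lesions | none | none |
| Attachment 5 category | SD (Table A) | Non-CR/Non-PD (non-target definitions; outside Table A) |
| In DCR numerator (SAP 6.5.3.3) | yes | no |
| In DCR denominator (ITT) | yes | yes |

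The second patient cannot reach PR or SD, since both are measured on target lesions. Only complete disappearance of the non-target disease, if called CR, would bring that patient into the numerator.

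**2. Size of the understatement**

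Inputs: N = 416 (Protocol 14.8; SAP 4.2). Assumed: share *f* without an IRC target lesion, 3–10%; proportion *p* of them Non-CR/Non-PD, 80%.

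- Patients without an IRC target lesion, N × *f*: 416 × 0.03 ≈ 12 and 416 × 0.10 ≈ 42.
- Understatement of DCR, *f* × *p*: 0.03 × 0.80 = 2.4 points and 0.10 × 0.80 = 8 points.

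**3. Effect on the comparison between arms**

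Suppose that *f* is equal in both arms, that patients with and without a target lesion have the same true control rate, and that all those without one count as failures. Each arm's rate, and the difference, is then multiplied by (1 − *f*). With assumed true rates of 75% and 85% (difference 10 points):

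- *f* = 5%: 75 × 0.95 = 71.25% and 85 × 0.95 = 80.75%; difference 9.5 points.
- *f* = 10%: 75 × 0.90 = 67.5% and 85 × 0.90 = 76.5%; difference 9.0 points.

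The level of DCR moves more than the contrast between arms.

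**4. Sample size is not in question**

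The plan's 262 PFS events reproduce. For HR 0.69, 2-sided alpha 0.05 and power 0.85, Schoenfeld's formula gives 4 × (1.960 + 1.036)² / (ln 0.69)² ≈ 261. Power at 262 events is 0.852. Nothing in the DCR definition enters that calculation.

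**The case against.** **The IRC's coding rules are not in the documents.** Protocol 10.6.9 ties Attachment 5 to the investigators' local reads. Protocol 14.2 and SAP 5.1 say that the IRC uses RECIST 1.1 and leave further methods to the IRC Charter, which was not supplied. This stands as a limit on what can be said about IRC labels. It does not rescue the DCR definition: the Charter can settle which label a patient receives, but the SAP fixes which labels count. A Charter rule calling such visits SD would depart from the definition of SD in Attachment 5, and the SAP would still need to say so.

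**Counting Non-CR/Non-PD as disease control is partly a choice of definition.** That is fair, and a sponsor could choose otherwise. But the plan gives no reason for the exclusion, and Table A gives SD to the same non-target picture whenever a stable target is present.

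**The share is unanchored.** This also stands. Attachment 5 treats lesions in previously irradiated or locally treated areas as non-measurable. That could create disagreement where an investigator overlooks it, or reduce disagreement because the rule is fixed.

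**A stronger inference, about primary PFS.** A reader might infer that these patients would be coded non-evaluable. SAP Table 4 counts as missed visits those "including missing assessments, insufficient data for the assessments, and an overall response of non-evaluable", so their later PFS events would be censored. The documents do not support this:

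- Table A excludes patients without targets; it does not return NE for them. Its row for targets not all evaluated presupposes that targets exist.
- Attachment 5 reserves not evaluable for visits with no imaging or with only some lesions measured. A fully imaged patient with non-target disease only meets neither condition.
- Non-CR/Non-PD is an assessment in its own right, and PD can be called from non-target disease or a new lesion.
- Even if every such visit were coded NE, Table 4 needs two in a row. With 8-weekly scans, PD at week 8 or 16 would still count. Week 16 is 3.68 months, so under the planning medians of 8 and 11.6 months about 27% and 20% of patients have had an event by then (mean 23.5%). That is about 37% of the 63% planned event ratio. Of the 8–26 events expected in 12–42 such patients (12 × 0.63 and 42 × 0.63), about 5–16 would be exposed, and only under a coding that no passage directs.

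**Conclusion.** The concern holds for DCR. As written, the SAP scores a non-progressing patient with persisting disease and no IRC target lesion as lacking disease control. The understatement is about 2.4–8 percentage points if 3–10% of patients have no IRC target lesion and 80% of these are Non-CR/Non-PD. Both inputs are assumptions, and the true share could lie outside the range or be close to zero.

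The point is minor. DCR is an additional endpoint, the alpha strategy in SAP 4.2 runs from PFS to OS only, and in a double-blind trial there is no evident reason for the share to differ by arm. No conclusion about primary PFS, the 262 events or the power follows from it.

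**What to change.** - In SAP 4.1.1.3 and 6.5.3.3, count Non-CR/Non-PD per IRC in the DCR numerator alongside SD.
- Keep the ITT denominator.
- Report, by arm, the number of patients in whom the IRC found no target lesion at baseline, so that the effect of the rule can be seen.

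The change is best made before unblinding. It costs a few words in the SAP and one added count, with no new data, readers or patients. Its one consequence is a slightly higher DCR in both arms. No change to SAP Table 4 or to the PFS analysis is needed on this account.

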ATTACHMENT 6: DRUG INTERACTIONS

Drug Interactions with CB-839

CYP2C9 Substrates with a narrow therapeutic index	Other CYP2C9 Substrates

 • S-Warfarin (anticoagulant) • Phenytoin (antiepileptic) 	
 • NSAIDs (analgesic, antipyretic, anti-inflammatory) 
 ○ celecoxib ○ lornoxicam ○ diclofenac ○ ibuprofen ○ naproxen ○ ketoprofen ○ piroxicam ○ meloxicam ○ suprofen • fluvastatin (statin) • sulfonylureas (antidiabetic) 
 ○ glipizide ○ glibenclamide ○ glimepiride ○ tolbutamide ○ glyburide • irbesartan/losartan • sildenafil (in erectile dysfunction) • terbinafine (antifungal) • amitriptyline (tricyclic antidepressant) • fluoxetine (SSRI antidepressant) • nateglinide (antidiabetic) • rosiglitazone (antidiabetic) • tamoxifen (SERM) • torasemide (loop diuretic) ketamine

*Narrow therapeutic index is defined as “CYP substrates with narrow therapeutic range refers to drugs whose exposure-response relationship indicates that small increases in their exposure levels by the concomitant use of CYP inhibitors may lead to serious safety concerns (e.g., Torsades de Pointes).”

<http://www.fda.gov/drugs/developmentapprovalprocess/developmentresources/druginteractionslabeling/ucm093664.htm>

Drug Interactions with Cabozantinib

CYP3A4 Inhibition on Cabozantinib

Administration of a strong CYP3A4 inhibitor, ketoconazole (400 mg daily for 27 days) to healthy patients increased single-dose plasma cabozantinib exposure (AUC_{0-inf}) by 38%. Concomitant use of cabozantinib with a strong CYP3A4 inhibitor **increased** the exposure of cabozantinib compared to the use of cabozantinib alone. Reduce the dosage of cabozantinib if concomitant use with strong CYP3A4 inhibitors cannot be avoided.

Examples include: boceprevir, clarithromycin, conivaptan, erythromycin, grapefruit juice, indinavir, itraconazole, ketoconazole, lopinavir/ritonavir, nefazodone, nelfinavir, posaconazole, ritonavir, saquinavir, telithromycin, verapamil, and voriconazole

CYP3A4 Induction on Cabozantinib

Administration of a strong CYP3A4 inducer, rifampin (600 mg daily for 31 days) to healthy patients decreased single-dose plasma cabozantinib exposure (AUC_{0-inf}) by 77%. Concomitant use of cabozantinib with a strong CYP3A4 inducer **decreased** the exposure of cabozantinib compared to the use of cabozantinib alone. Increase the dosage of cabozantinib if concomitant use with strong CYP3A4 inducers cannot be avoided.

Examples include: rifampin, phenytoin, carbamazepine, phenobarbital, rifabutin, rifapentine, and St. John's Wort

**ATTACHMENT 7: NCCN-FACIT MEASUREMENT SYSTEM (FKSI-19)
QUESTIONNAIRE/ SCALE**

Below is a list of statements that other people with your illness have said are important. **Please circle or mark one number per line to indicate your response as it applies to the past 7 days.**

		Not at all	A little bit	Some- what	Quite a bit	Very much	
D R S- P	GP1	I have a lack of energy	0	1	2	3	4
	GP4	I have pain	0	1	2	3	4
	C2	I am losing weight	0	1	2	3	4
	HI7	I feel fatigued	0	1	2	3	4
	B1	I have been short of breath	0	1	2	3	4
	BRM3	I am bothered by fevers (episodes of high body temperature)	0	1	2	3	4
	BP1	I have bone pain	0	1	2	3	4
	L2	I have been coughing	0	1	2	3	4
	HI12	I feel weak all over	0	1	2	3	4

D R S- E	RCC2	I have had blood in my urine	0	1	2	3	4
	C6	I have a good appetite	0	1	2	3	4
	GF5	I am sleeping well	0	1	2	3	4
	GF6	I worry that my condition will get worse	0	1	2	3	4
	GF2	I have nausea	0	1	2	3	4
	C5	I have diarrhea (diarrhoea)	0	1	2	3	4
T S E	GF5	I am bothered by side effects of treatment	0	1	2	3	4
	GF1	I am able to work (include work at home)	0	1	2	3	4
	GF3	I am able to enjoy life	0	1	2	3	4
F W B	GF7	I am content with the quality of my life right now	0	1	2	3	4

